**Figure 9 - American Heart Association Algorithm for Adult Cardiac Life Support**  
ETI or LT insertion may typically occur at boxes 6 and 10, "Consider advanced airway." EMS agencies will follow local ACLS protocols.

---

advanced-level EMS personnel will perform airway management (ETI, LT or BVM) during resuscitation as guided by local protocol or practice.

Upon arriving upon the scene of a potentially eligible subject, treating EMS personnel will initiate resuscitation measures per local BLS and ACLS protocol. Patient assessment, initiation and style of chest compressions, rhythm assessment, shock delivery, intravenous line insertion, and drug administration will be performed according to local protocol and practices.

Simultaneously, EMS personnel will verify eligibility for the trial (i.e., satisfaction of inclusion criteria and absence of any exclusion criteria).

At the point where they are ready to perform advanced airway insertion, EMS personnel will select the airway management technique to which they have been randomized (ETI or LT). EMS personnel will perform ETI or LT insertion using techniques consistent with local protocol.

EMS personnel will verify successful and correct placement of the ET tube or LT according to local protocols. Customary methods for confirming tube placement including physical examination (chest rise), auscultation of chest for presence of breath sounds, auscultation of epigastrium for absence of gastric sounds, use of a bulb syringe detection, use of a colorimetric end-tidal carbon dioxide detector, and use of a waveform digital end-tidal carbon dioxide detector.

EMS personnel will secure airway device in place per local protocol. Standard methods for securing the ET tube and LT airway include adhesive tape, umbilical “twill” tape and commercial tube holders. Of note, the LT cannot be secured using an ET tube commercial tube holder; rescuers should use adhesive tube or a tube holder designed for the larger diameter of the LT.

After securing the airway device, EMS personnel will continue with standard resuscitation measures. Decisions for termination of resuscitation in the field or transporting to receiving Emergency Department are not dictated by this trial.

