## **12.5 Protocol Considerations**

### **12.5.1 Number of Airway Insertion Attempts**

Successful ETI or LT insertion may require multiple attempts. With “attempt” defined as passage of the laryngoscope blade into the mouth, Wang, et al. observed that first-attempt success for paramedic ETI of OHCA was 70%, with up to four attempts needed to reach the 90% success threshold. EMS practitioners generally try to minimize the number of ETI attempts because of the propensity of oral injury and because multiple attempts may signal ETI futility and the need to proceed to alternate airway management techniques. In clinical practice, some EMS protocols limit practitioners to 3, 2 or even 1 unsuccessful ETI attempt before proceeding to alternate “rescue” airway measures.

This trial will not dictate or limit the number of ET tube or LT insertion attempts. However, we will monitor the number of insertion attempts for each device. Training for the trial will emphasize a)

definition of “ETI attempt” as insertion of laryngoscope between the teeth (not insertion of ET tube), b) definition of “LT attempt” as insertion of LT airway between the teeth, c) methods for reporting the number of attempts for each airway device, and d) strategies for minimizing ETI or LT insertion attempts.

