- **Airway swelling or edema.** A described complication of the LT is the development of major tongue, pharyngeal or hypopharyngeal swelling, which may interfere with ventilation. While usually associated with instances of prolonged LT ventilation (several hours), some clinicians have reported the occurrence of this event during resuscitative efforts. This event

will be based upon EMS and ED personnel assessment and will be determined from EMS and ED patient care records. The timeframe for surveillance for this event will be limited to the earlier of a) replacement of the LT with an ET tube, or b) the first 24 hours of hospitalization. While generally associated with LT insertion, we will monitor the occurrence of airway swelling or edema regardless of inserted airway device.

- **Oropharyngeal or hypopharyngeal injury.** Advanced airway insertion may result in injury to the oropharynx and hypopharynx, including soft tissue lacerations, injury to teeth, and perforation of pharyngeal, hypopharyngeal or other anatomic structures, among others. This event will be determined by review of the discharge summary and ED physician records and will be limited to injuries identified during the first 24 hours of hospitalization.
- **Pneumothorax.** Airway insertion and ventilatory efforts may cause pulmonary barotrauma, resulting in pneumothorax. This event will be determined from radiology or ED physician interpretation of the first chest x-ray or computed tomography (CT) performed in the ED.
- **Pneumonia and aspiration pneumonitis.** Pneumonia and aspiration pneumonitis are known sequelae of cardiac arrest and airway management. This event will be defined as the presence of an infiltrate or consolidation as reported by radiology interpretation of chest x-rays or computed tomography (CT) performed during the first 72 hours of hospitalization.

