## 20. EMS Research Protocol Training

### 20.1 Overview of EMS Protocol Training Elements

Training of EMS personnel for this trial will encompass didactic and practical modalities. The salient components of EMS personnel training are described below. While we will develop a master set of training materials, individual regional coordinating centers will be permitted to customize the format to suit local needs.

Prior to entering the trial, participating EMS agencies will summarize their experience with and standard training practices (format, frequency) for both airway devices.

All participating EMS agencies will receive initial training in the trial protocol. Key elements of training will include:

- **Scientific Basis for the Trial** – This section include level-appropriate presentation of the scientific principles of airway management, a summary of prior studies of OHCA airway management, and the rationale for the current randomized trial. All EMS personnel that may potentially carry out study procedures will be required to undergo training.
- **Review of Study Protocol** – This section will include the following: overall study design, inclusion and exclusion criteria, the process of exception to informed consent under

emergency circumstances, the study protocol and procedures, data reporting, and contingency measures.

- **Protocol Practicum** – EMS personnel will have the opportunity to simulate execution of the trial protocol in “hands-on” fashion. This practical experience will encompass the use of mannequins that can accommodate ETI and LT insertion. EMS personnel will be given the opportunity to practice to proficiency each component of the protocol. EMS personnel will have the opportunity to integrate the trial procedures in the context of other ACLS interventions. Various permutations of the study protocol will be presented, including each of the study arms and scenarios with unsuccessful initial airway attempts.
- **Data Reporting** – Select data elements specific to airway management are required for this trial; for example, the sequence of airway interventions, the number of attempts, the timing of successful airway insertion, and adverse events. The training will review definitions and reporting practices for each of these data elements.

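### Oropharyngeal and hypopharyngeal injury is counted only from hospital records, so a patient whose resuscitation ends on scene cannot have the event even if the crew documents it

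*Combined protocol and SAP*

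**What the plan says.** Section 14.3.2 describes the event as a consequence of airway insertion: "Advanced airway insertion may result in injury to the oropharynx and hypopharynx, including soft tissue lacerations, injury to teeth", together with perforation of nearby structures. It sets the source and the window in one sentence: the event "will be determined by review of the discharge summary and ED physician records and will be limited to injuries identified" within the first 24 hours in hospital. EMS records are not mentioned.

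The item just before it in the same section, airway swelling or edema, "will be based upon EMS and ED personnel assessment and will be determined from EMS and ED patient care records".

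Section 12.4 states: "Decisions for termination of resuscitation in the field or transporting to receiving Emergency Department are not dictated by this trial". Section 12.5.6 expects most patients to reach an ED but gives no figure.

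Section 19.1 provides for review of all EMS and hospital records. Section 20.1 trains crews to report data elements that include "the number of attempts, the timing of successful airway insertion, and adverse events".

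Section 22.2 asks clinical staff to report every potential adverse event to the coordinating center. It then ties the recording of expected adverse events to the hospital discharge summary.

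The Summary (Section 3) lists oropharyngeal and hypopharyngeal trauma within the Adverse Events secondary outcome. Section 15.4 says the secondary outcomes are analysed in a similar manner to the primary one.

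**The concern.** The trial's interventions are delivered in the field, and Section 12.5.1 notes that EMS practitioners limit ETI attempts "because of the propensity of oral injury". Yet ascertainment of that injury begins only at the hospital. A tooth injury or laceration noted by the crew is not an event if the patient is pronounced dead on scene. In a transported patient it is not an event unless the ED physician record or the discharge summary also carries it.

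The count is therefore incomplete over the enrolled population for a named component of a secondary outcome. Safety outcomes by arm are also among the factors that Section 16.2 lists for stopping decisions. If the share terminated in the field differed by arm, the reported injury rates could differ with no difference in injury.

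**Working it through.** **Text check.** Sources and windows in Section 14.3.2, side by side:

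| Event | Source named | Can a patient who dies on scene have it? |
|---|---|---|
| Unsuccessful insertion | EMS | Yes |
| Multiple attempts | EMS | Yes |
| Misplacement or dislodgement (ETI only) | EMS and ED | Yes |
| Inadequate ventilation | EMS | Yes |
| Airway swelling or edema | EMS and ED | Yes |
| **Oropharyngeal or hypopharyngeal injury** | **ED physician record, discharge summary** | **No** |
| Pneumothorax | ED chest x-ray or CT | No (imaging needed) |
| Pneumonia or pneumonitis | Hospital chest imaging | No (imaging needed) |

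Injury is the only event in the list that needs no imaging and still omits EMS records. Its source rule and its window each exclude a patient who never reaches hospital. The general reporting route in Section 22.2 does not close the gap. A crew report made that way would not meet the Section 14.3.2 definition, and Section 22.2 itself sends expected events back to the discharge summary.

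**Size.** The plan gives no figure for this event, so there is nothing to reproduce. The termination share and the injury risk below are assumptions. The 1,306 per arm is from Section 16.1.

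*Capture.* Let t be the share terminated on scene, with the same injury risk p in terminated and transported patients. The largest share of injuries that hospital sources can capture is (1 − t)p / p = 1 − t.

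- t = 20%: 80%
- t = 30%: 70%
- t = 40%: 60%

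With p = 4%, an arm has 1,306 × 0.04 ≈ 52 injuries. At most about 42, 37 or 31 of them could be counted. These are ceilings, since hospital records will also miss some injuries in transported patients.

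*Arm comparison.* Take p = 4% in both arms, with 30% terminated under ETI and 25% under LT.

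- Reported rates per enrolled patient: 0.70 × 4% = 2.8% and 0.75 × 4% = 3.0%, or about 37 and 39 patients of 1,306.
- Standard error, ignoring clustering: √[(0.028 × 0.972 + 0.030 × 0.970) / 1,306] ≈ 0.66 percentage points.
- Difference: 0.2 / 0.66 ≈ 0.3 standard errors.
- Per transported patient: 2.8 / 0.70 = 4% and 3.0 / 0.75 = 4%, so the difference disappears, at the price of conditioning on transport, which occurs after assignment.

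**The case against.** Using hospital physicians as the source is defensible. ETI exposes the airway under a lighted laryngoscope (Section 12.2.1), whereas the LT goes in blindly (Section 12.3.1). Crews are unblinded (Section 13.3) and would be reporting injuries from their own procedures. Crew records may therefore detect injury unequally by arm. This stands. It calls for separate reporting by source, which makes the problem visible but does not remove it.

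A reader might infer that usable data are already being collected and thrown away. The documents do not show this. Section 20.1 trains crews to report adverse events in general terms, and the EMS airway variables in Section 14.2.2 are sequence, success, attempts and time. Nothing says that crews look for or record oral injury, and a perforation may not be apparent during CPR.

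A reader might also infer that injuries concentrate in patients terminated on scene, so that the loss is worse than proportional. Section 12.5.1 links attempts to oral injury, but no section links attempts to field termination, so a raised risk in that group is unsupported.

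Nor does the event consist only of field injuries. Its definition speaks of advanced airway insertion and, unlike several neighbouring items, does not exclude insertion in the ED.

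Finally, the stakes are limited. Section 14.3.2 says these events are monitored and reported but not treated as adverse events of the intervention. A serious scene injury could still reach safety review through the open reporting form in Section 22.2. That softens the consequence without repairing the tabulated outcome.

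**Conclusion.** The gap is real and follows from the text alone: as defined, this event cannot occur in a patient whose resuscitation ends on scene, and in transported patients it depends on a hospital record. The main effect is under-ascertainment. If 20% to 40% are terminated on scene with equal risk, the ceiling on capture is 80% to 60%. How much of the remainder EMS records would recover is unknown, because the documents give no rate of crew-recorded injury.

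It would be tempting to conclude that the rule produces a misleading difference between arms. That is possible only if termination differs by arm and rates are reported per enrolled patient. Neither is established, since Section 15.4 does not state the denominator for this event, and the illustrative distortion is small against sampling error. The primary outcome, sample size and stopping boundaries are untouched. This should be corrected, but it does not threaten the trial's main conclusion.

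**What to change.** - In Section 14.3.2, add EMS patient care records to the ED physician record and discharge summary as sources for this event. Start the window at EMS airway management and end it 24 hours into hospitalization.
- In Section 22.2, align the sentence on recording expected adverse events, so that it no longer points to the discharge summary alone.
- Report counts by arm, by source and by whether the patient was transported. Keep the hospital-only count among transported patients as a separate line, with its denominator stated.
- State that the EMS-sourced comparison between arms is to be read with caution, for the detection reason given above.

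The change concerns measurement only and leaves clinical care as it is. EMS records are already reviewed, so the cost is modest, but it may be more than a wording edit. Consistent capture may need one added field on the EMS form, with an abstraction rule and a line in retraining. If that field is made a required element, it falls under the limit on missing entries in Appendix 3. Crew notes will remain incomplete and unblinded.

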#### 14.4 Other Data

Additional data will be collected from the out-of-hospital, Emergency Department and hospital care phases.

##### 14.4.1 CPR Process Data

All participating ROC EMS units have automated external defibrillators (AED) and/or manual monitor/defibrillators capable of monitoring individual components of CPR process; for example, the delivery of individual chest compressions, chest compression rate, interruptions, and fraction, and (in select cases) chest compression depth. Currently, all CPR process data files are uploaded to the UW CTC. While this archiving process will continue during the study (in order to allow for rhythm audits), CPR process data analysis will not be part of this trial. However, additional grants may provide funding for the review of the electronic ECG, entry of data into the database, analysis of CPR process data and selected audits.

##### 14.4.2 Other Explanatory Mechanisms

Physiologic mechanisms hypothesized to influence OHCA outcomes after paramedic airway management include CPR interruptions, hyperventilation, and carotid artery impingement. This trial focuses on pragmatic outcomes and will not examine these mechanisms.

## 15. Analysis Plan

### 15.1 CONSORT Diagram

Figure 12 provides the anticipated CONSORT Diagram for the trial. The trial will exclude OHCA that do not meet inclusion criteria, as well as those who do not require ventilatory support. The remaining subjects will be enrolled and randomized in the trial.

### 15.2 Intention-to-Treat vs As-Treated

The intention-to-treat comparison will include the two treatment arms: primary-ETI and primary-LT. Where allowed by local protocol, the primary-LT arm will allow for BLS LT insertion.

The as-treated comparison will encompass the initial advanced airway technique received by the subject, whether the airway insertion is successful or unsuccessful. Practically, this will account for situations where randomization is violated; for example, use of the ETI when the patient is randomized to primary-LT, or BLS rescuer use of LT when the patient is assigned to primary-ETI (and hence BLS BVM). In cases where rescuers use only BVM (without resorting to ETI or LT insertion), this will not be considered a protocol violation, and the subject will be retained in the assigned randomization. In cases where rescuers use a different technique as the initial airway intervention (other than ETI or LT), the subject will be excluded from the as-treated analysis.

While this trial focuses on two airway management strategies (primary-ETI and primary-LT), in execution the course of airway management may encompass other airway management endpoints, including BVM ventilation, use of ETI other than orotracheal technique, use of a SG other than LT, or use of an another airway management technique (for example, cricothyroidotomy). Also, airway insertion efforts may prove unsuccessful, necessitating the use of alternate airway techniques. Therefore, a second as-treated comparison will consider the final result of EMS airway management efforts: a) ETI, b) LT, c) BVM, and d) other airway technique.

### 15.3 Primary Analysis – 72-Hour Survival

The primary hypothesis is that there is no difference in OHCA 72-hour survival between primary LT- and primary-ETI airway management strategies. The primary outcome of interest is 72-hour survival. We will calculate the difference in outcomes divided by the estimated “robust” standard error based on the Huber-White sandwich estimator in order to account for within cluster correlation and variability, which might depart from the classical assumptions. To quantify the treatment effect, we will calculate the 95% CI for the difference in event rates. Since

[figure not shown]

Figure 12 - Anticipated CONSORT Diagram

randomization includes all eligible OHCA patients, we will not stratify the primary analysis by initial cardiac rhythm. We will perform the analysis on intention-to-treat (primary) as well as as-treated (secondary) bases.

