### Outcomes:

The primary outcome will be:

- 1) **72-hour hospital survival**, defined as patient status (alive/dead) at 72 hours after the initial onset of cardiac arrest.

Secondary outcomes will include:

- 1) **Return of Spontaneous Circulation (ROSC)**, defined as the presence of palpable pulses upon ED arrival.
- 2) **Airway Management Clinical Course**, including sequence of ETI/LT insertion, ETI/LT insertion success and time, number of ETI/LT insertion attempts, and airway conversion (change of LT-to-ETI, or ETI-to-LT) in the receiving Emergency Department.
- 3) **Adverse Events**, including initially unrecognized airway misplacement (including endotracheal tube misplacement), inadequate ventilation requiring airway exchange, vomiting, oropharyngeal, hypopharyngeal or gastrointestinal trauma, and pneumothorax.
- 4) **Hospital Survival**, defined as patient status (alive/dead) at hospital discharge.

- 5) **Hospital Survival with Good Neurologic Function**, defined as Modified Rankin Score  $\leq 3$  upon hospital discharge.

**Analysis:** We will calculate the difference in outcomes divided by the estimated “robust” standard error based on the Huber-White sandwich estimator in order to account for within cluster correlation and variability, which might depart from the classical assumptions. To quantify the treatment effect, we will calculate the 95% CI for the difference in event rates. We will perform the analysis on an intention-to-treat (primary analysis) as well as treatment-received bases (secondary analysis).

**Sample Size:** The trial will require 2,612 subjects (1,306 per group) to have 85% power to detect a 4.5% absolute difference in 72-hour survival, given baseline survival of 13.7% and an overall two-sided alpha of 0.05. To allow for subject withdrawal and lost-to-follow-up, the trial will enroll up to 3,000 subjects.

**Regulatory and Ethical Considerations:** The trial will be carried out under federal rules for Exception from Informed Consent (EFIC) outlined by the guidance document “Waiver of Informed Consent Requirements in Certain Emergency Research” (Federal Register, Vol. 61, pp. 51531-51533, November 1, 1996 - <http://www.gpo.gov/fdsys/pkg/FR-1996-10-02/html/96-24968.htm>), OHRP “Basic HHS Policy for Protection of Human Research Subjects” (45 CFR 46.101(i) - <http://www.hhs.gov/ohrp/humansubjects/guidance/45cfr46.html#46.101>), and FDA regulations 21 CFR 50.24.

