### 13. Random Allocation and Blinding

#### 13.1 Random Allocation Method

The airway intervention will be cluster randomized at the EMS agency level with periodic crossover. Each site will be subdivided into multiple clusters by EMS agency, station, or other unit as appropriate to the site’s EMS structure. Each cluster will be scheduled to crossover to the opposite treatment – typically once or twice per year during the trial. The use of crossovers is efficient and minimizes unbalanced treatment assignment.

If more than one participating EMS agency is present on scene, the first arriving unit will determine the study treatment assignment. If a non-ROC EMS agency arrives first on scene, the subsequent first arriving ROC EMS agency will perform airway management as randomized.

The randomization of clusters will be stratified by site. Within each site, clusters will be organized into relatively homogeneous groups with respect to the number of patients expected to be treated over the course of the study in that cluster. All clusters will crossover between intervention assignments at least once (i.e., have at least two distinct treatment periods). If necessary, some clusters with high episode rates will crossover more than once.

Random assignment of treatment sequence will be performed by the coordinating center prior to the start of the study.

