**Table 4 - Sample Size Estimates**  
Effect sizes based upon 13.7% baseline 72-hour survival.

in 72-hour survival after OHCA, with an overall significance level (adjusted for interim analyses) of 0.05 and accommodating up to a 5% loss of precision due to cluster randomization (with crossover).

The estimated effect sizes are based upon observations from the ROC PRIMED Trial. In ROC PRIMED, baseline 72-hour survival was 13.7%. There was a 5.0% absolute difference in 72-hour survival between ETI (13.7%) and SGA (8.7%). To account for potential confounders, for this trial we will use a more conservative figure of 4.5% to represent a minimal clinically significant difference. We designed the trial to have 85% power to detect this difference. Therefore, the required minimum sample size is 2,612 subjects (1,306 per group). To allow for subject withdrawal and loss to follow-up, we have budgeted to enroll up to a total of 3,000 subjects.

The participating US ROC sites (Alabama, Dallas, Milwaukee, Pittsburgh, Portland and San Diego) historically treated over 3,000 OHCA requiring advanced airway management in 2013. Therefore, we expect to have adequate capacity to enroll the requisite number of subjects over the anticipated three-year study period.

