## 16.2 Interim Monitoring Plan and Stopping Boundaries – Criteria for Terminating the Trial

With input from the Data Safety and Monitoring Board (DSMB), prior to initiation of the trial, we will develop a monitoring plan to guide early termination of the trial. Factors influencing stopping decision may include (a) formal stopping rules based upon the primary analysis, (b) information on safety outcomes by treatment group, (c) consistency between results for primary and secondary outcomes, and (d) consistency of treatment effects across subgroups.

			Lower Stopping Boundary (SGA Better)			
Analysis	Cum. Sample Size	Prop. Max Stat Info	Absolute Difference	Adjusted Difference	95% Confidence Interval	P-value
1	654	0.25	-0.108	-0.098	(-0.154, -0.041)	0.001
2	1,306	0.50	-0.102	-0.092	(-0.135, -0.053)	<0.001
3	1,958	0.75	-0.092	-0.084	(-0.120, -0.052)	<0.001
4	2,612	1.00	-0.029	-0.029	(-0.059, 0.000)	0.050

			Upper Stopping Boundary (ETI Better)			
Analysis	Cum. Sample Size	Prop. Max Stat Info	Absolute Difference	Adjusted Difference	95% Confidence Interval	P-value
1	654	0.25	0.125	0.116	(0.058, 0.172)	<0.001
2	1,306	0.50	0.118	0.109	(0.069, 0.151)	<0.001
3	1,958	0.75	0.106	0.099	(0.066, 0.135)	<0.001
4	2,612	1.00	0.029	0.029	(0.000, 0.059)	0.050

Table 5 - Interim Stopping Boundaries for 72-Hour Survival

The formal stopping boundaries are asymmetric, two-sided designs which are included in the unified family of group sequential stopping rules. (Table 5) The boundaries are asymmetric, because the utility/ease of use/training for a SGA is judged to be preferable to ETI. The tests for

superiority of either intervention will be based upon boundaries with parameters  $P=(0,0)$ ,  $R=(0.2,0.2)$ ,  $A=(0.355,0.29)$ , and  $\epsilon=c(1,1)$ , with a two-sided overall alpha level of 0.05.

We envision conducting 4 total analyses (3 interim + 1 final). The study does not include any futility boundaries because obtaining estimates in either direction will be informative; even an estimate that both treatments yield similar 72-hour survival is informative.

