## **18.2 Milestones for Trial Execution and Subject Recruitment**

Trial execution and subject recruitment will occur over the 4-year period August 1, 2015 – July 30, 2019.

We expect 6 ROC regional coordinating centers encompassing over 33 EMS agencies to participate in the trial. We expect participating EMS agencies to complete a brief period (2-4 months) of data collection to demonstrate readiness for the enrollment phase of the trial. We expect recruitment of subjects to occur through July 30, 2018 (3 years). Trial close-out and analysis will occur during August 1, 2018 – July 30, 2019.

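### The primary test rests on a sandwich standard error with no stated clustering level, small-sample correction or reference distribution; used uncorrected against 1.96 at about 33 clusters, its two-sided error is about 6-8%, not 5%

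*Combined protocol and SAP*

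**What the plan says.** - **Test statistic.** Section 15.3, repeated in the Section 3 summary, divides the difference by a "standard error based on the Huber-White sandwich estimator in order to account for within cluster correlation and variability". Section 15.4 carries the same approach to the secondary outcomes.
- **Error rate.** The group sequential boundaries in Section 16.2 are set "with a two-sided overall alpha level of 0.05". The final row of Table 5 has a boundary of 0.029, an interval from 0.000 to 0.059 and p = 0.050. Section 16.2 adjusts the final estimate, interval and p-value for the stopping rule only.
- **Clusters.** Section 13.1 opens with "The airway intervention will be cluster randomized at the EMS agency level with periodic crossover", then says "Each site will be subdivided into multiple clusters by EMS agency, station, or other unit as appropriate". Section 18.2 states "We expect 6 ROC regional coordinating centers encompassing over 33 EMS agencies to participate in the trial". No section gives the number of clusters.
- **Not stated anywhere:** the level at which the standard error is clustered, a finite-cluster correction, degrees of freedom, a reference distribution, an intracluster correlation (ICC), or the spread of cluster sizes. Section 13.1 does say that some clusters have high episode rates, so sizes will be unequal.

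**The concern.** The sandwich variance is justified as the number of clusters grows large. With a few dozen clusters it is on average too small, more so when sizes are unequal, and 1.96 ignores the uncertainty in estimating it. Both effects make the test reject too often and the interval too narrow.

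The clustering level matters as well. In a crossover, treating each cluster-period as independent ignores the correlation between periods of the same cluster, which pushes the error the other way. Two analysts could both follow Section 15.3 and run tests with materially different error rates. The choice affects the primary p-value and interval, and presumably the interim looks and secondary outcomes.

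**Working it through.** **1. Reproduce the plan's figures.** The summary asks for "85% power to detect a 4.5% absolute difference in 72-hour survival, given baseline survival of 13.7% and an overall two-sided alpha of 0.05"; Section 16.1 gives 2,612 patients and allows up to a 5% loss of precision for clustering.

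- Variance sum for 13.7% vs 18.2%: 0.137 x 0.863 + 0.182 x 0.818 = 0.2671.
- Per group: (1.960 + 1.036)^2 x 0.2671 / 0.045^2 = 1,184, or 2,369 in total.
- 2,369 x 1.05 = 2,487, and 2,369 x 1.05^2 = 2,611 (stated: 2,612). The factor 1.05^2 is inferred. It could be a 5% larger standard error, or 5% for clustering plus about 5% for interim looks.
- Implied standard error: 1.05 x sqrt(0.2671 / 1,306) = 0.01502.
- Final boundary with z: 1.96 x 0.01502 = 0.0294, against 0.029 in Table 5. With t on 32 df: 2.037 x 0.01502 = 0.0306.

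The design arithmetic therefore fits a normal critical value. This supports, but does not prove, a normal reference in the analysis.

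**2. Equal cluster sizes, analytic.** With G equal, balanced crossover clusters, the uncorrected sandwich variance is (G - 1)/G times the usual variance of the mean cluster difference. The two-sided error against 1.96 is 2 x P(t on G - 1 df > 1.96 x sqrt((G - 1)/G)).

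- G = 33: 6.25%
- G = 60: 5.7%
- G = 100: 5.4%

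**3. Unequal sizes, simulation under no effect.** From the plan: N = 2,612, 13.7% survival, at least two periods per cluster. Assumed: gamma-distributed cluster sizes with the coefficient of variation (CV) shown; base ICC 0.01 with a further period ICC of 0.002, varied over 0-0.03 and 0-0.01; 2 to 6 periods. There were 20,000 replicates per setting (Monte Carlo margin about 0.35 points) and one final look. The test used the uncorrected standard error, clustered on the randomized unit, against 1.96.

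| Clusters | Size CV | Two-sided error |
|---|---|---|
| 33 | 0 | 6.1-6.6% |
| 33 | 0.5 | 6.6% |
| 33 | 0.7 | 6.4-7.1% |
| 33 | 1.0 | 7.2-8.0% |
| 33 | 1.3 | 8.2% |
| 45 | 0 to 1.3 | 6.0-7.4% |
| 60 | 0 to 1.3 | 5.5-7.0% |
| 100 | 0 to 1.3 | 5.2-6.0% |

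ICC and number of periods change the result little; cluster count and size variation drive it.

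**4. Clustering on cluster-period instead.** With 33 clusters and the base ICCs the error is about 2.4-4.0%, rising with the number of periods. That test is conservative.

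**5. Candidate corrections at 33 clusters.**

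- G/(G - 1) correction with t on 32 df: 5.1% with equal sizes, 5.4-5.8% at CV 0.7, about 6.2% at CV 1.0, 6.7% at CV 1.3.
- Leave-one-cluster-out standard error with t on (clusters - 1) df: about 4.6-6.0%. It stays in that range up to 100 clusters.

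**The case against.** **The plan does not say that the standard error is uncorrected or the reference normal.** This stands. Both are inferred from silence and from Table 5, which holds design-stage boundaries; Section 16.2 says the monitoring plan is still to be developed with the DSMB. The defect is an unspecified test, not a documented wrong one.

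**33 is not the number of clusters.** This also stands. It is a floor on agencies. Dividing agencies into stations would raise the count and shrink the excess to about 5-7% at 60 to 100 clusters. Suspension of agencies under Appendix 3 could lower the number contributing.

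**The planned randomization may help.** Section 13.1 stratifies by site and groups clusters by expected volume. In simulations with 33 clusters and size CV 0.8, pairing by volume gave 6.5-6.9%, against 6.9-7.3% without it. Adding a 3-point secular trend to the paired design gave 6.7% with four periods and 5.2% with two. The excess is therefore modest and in some settings nearly absent.

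**The direction is not guaranteed.** Correct: clustering on cluster-period would make the test conservative. That is a further reason to fix the level in advance.

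A reader might go further and infer that the plan prescribes a test with an error of 7-8%, or above 10%. The documents do not support this. At 33 clusters, 7-8% needs markedly unequal sizes. An error above 10% needs roughly 12 to 20 unequal clusters, and nothing in the documents points to so few.

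**Conclusion.** The gap is real and should be fixed. For its primary test the plan omits the number of clusters, the clustering level, any finite-cluster correction and the reference distribution, while claiming an overall two-sided 0.05. The size is conditional. If the standard error is clustered on the randomized unit and used uncorrected against 1.96, the error is about 6-8% at 33 clusters and about 5-7% at 60 to 100.

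This rests on assumed cluster-size variation and, to a small degree, on assumed ICCs. It covers the final analysis alone; the interim looks were not simulated. It is a moderate miscalibration that can be removed in advance, and it does not invalidate the design.

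**What to change.** In Sections 15.3 and 16.2, state:

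1. The number of clusters, in total and by site, and what the unit is at each site.
2. That the standard error is clustered on the randomized unit, not on cluster-period.
3. A bias-corrected sandwich, for example leave-one-cluster-out (CR3) or Mancl-DeRouen, with a t reference on (number of clusters - 1) degrees of freedom. The simple G/(G - 1) correction is weaker when sizes are very unequal.
4. That the same standard error and reference apply to the primary outcome, the interim looks and the secondary outcomes.

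A re-randomization test that follows the site-stratified treatment sequences can serve as a check.

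**Cost.** SAP wording and standard software. At 33 clusters the t value widens the interval by 2.037/1.96 = 1.039. A corrected standard error about 2-5% larger brings this to 1.039 x 1.02 = 1.06 up to 1.039 x 1.05 = 1.09, so about 6-9% wider. Power falls by about 2-3 points: the t reference alone gives Phi(2.997 - 2.037) = 83% against 85%, and one simulation with both changes went from 87% to 84%. In a further simulation (size CV 1.0, 8,000 replicates) the drop was about 4 points, from 85.5% to 81.6% with two periods. Part of this loss is only apparent, because the uncorrected test gains power by rejecting too often.
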